#### 4.3.1.2.5 Duration

Duration is derived from the start and end dates of the unsolicited AE:

- Duration = End date of unsolicited AE - start date of unsolicited AE + 1.

The duration should be considered as missing only if one or both of the start and end dates of the unsolicited AE is missing or partially missing.

#### 4.3.1.2.6 SAEs

An event will be considered as a serious event if “Yes” is checked for “Serious” in the CRF.

SAEs will be analyzed throughout the study using at least the following periods:

- Within 30 days after (each) injection
- During post-Dose i period (ie, between injection i and injection i+1 [for each injection except for the last one of the primary series], and within 30 days after the last injection of the primary series for Infant)
- During the 6-month follow-up period (ie, from 31 days after the last injection until the last participant contact)
- During the study (ie, all SAEs occurred during the study)

#### 4.3.1.2.7 AESIs

An event will be considered as an AESI if “Yes” is checked for “Is the event an AESI?” in the CRF.

AESIs will be analyzed throughout the study using the following periods:

- Within 30 days after (each) injection
- During post-Dose i period (ie, between injection i and injection i+1 [for each injection except for the last one of the primary series], and within 30 days after the last injection of the primary series for Infant)
- During the 6-month follow-up period (ie, from 31 days after the last injection until the last participant contact)
- During the study (ie, all AESIs occurred during the study)

#### 4.3.1.3 Other Safety Endpoints

##### 4.3.1.3.1 Injection Site Necrosis and Exfoliative Dermatitis

For the purpose of the Early Safety Data Review (ESDR) conducted by the SMT/DMC, a specific focus will be done on the following events: Injection site necrosis and Exfoliative dermatitis. These events will be identified also in the main statistical analysis among reported unsolicited AE using the following MedDRA preferred terms:

	MedDRA 23.1 preferred terms
Injection site necrosis	Injection site necrosis, Vaccination site necrosis, Application site necrosis, Extremity necrosis, Necrosis, Soft tissue necrosis, Administration site necrosis, Skin necrosis
Exfoliative dermatitis	Dermatitis exfoliative, Dermatitis exfoliative generalised, Exfoliative rash, Injection site rash, Vaccination site rash, Application site rash, Injection site dermatitis, Vaccination site dermatitis, Application site dermatitis, Administration site dermatitis

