5.1.6 Early Safety Data Review

The safety of investigational products will be continuously monitored by the Sponsor. An ESDR will be performed, the goal of which is to allow for a cautious, stepwise approach to vaccine administration.

The safety data collected will be entered into the CRB and summarized by the Sponsor. A blinded review will be performed by the SMT meetings. An unblinded review by the independent DMC will also be conducted. It is understood that this review is based on preliminary data that have not been subject to validation and database lock. The usual and ongoing process of monitoring safety signals outside of those specified in the protocol-defined early interim safety analysis will continue unchanged.

The following safety parameters will be assessed as part of the ESDR:

- Immediate unsolicited systemic AEs
- Solicited injection site and systemic reactions
- Unsolicited AEs reported as related by the Investigator
- SAEs
- AESIs

Enrollment of infants will not begin until the end of the review. In addition, the data will be examined for the following:

- Any deaths, regardless of causality
- Any vaccine-related SAEs
- AESIs
- Any signs of injection site necrosis or exfoliative dermatitis
- Grade 3 fever reported in more than 10% of subjects; presence of concurrent infectious disease will be documented.

If any of the above criteria are met, a decision based on the SMT and DMC recommendations will be made as to whether enrollment of infants will be allowed to begin or whether any adjustments ought to be done (eg, an SP0202 formulation should not enter Stage II of the study).

The DMC will review the unblinded data by group to be able to identify any trend for differences between each SP0202 formulation and Prevnar 13 for each safety criterion and overall safety profile. The DMC may recommend removing 1 or more SP0202 formulation from Stage II.

Moreover, the option of partial or full unblinding can be available to the Sponsor through an independent statistician, if required, for a further in-depth review of the data.

The Sponsor's SMT is empowered to recommend a pause in recruitment while it investigates any potential signal or concern. The clinical team and SMT will review the data being generated from the study at regular intervals for any new safety signals or safety concerns.

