9.1.1.3.5 Assessment of Causality

The Investigator will assess the *causal relationship* between each unsolicited systemic AE and the investigational product administered as either *not related* or *related*, based on the following definitions:

Not related – The AE is clearly / most probably caused by other etiologies such as an underlying condition, therapeutic intervention, or concomitant therapy; or the delay between vaccination and the onset of the AE is incompatible with a causal relationship; or the AE started before the first vaccination (screening phase, if applicable)

Related – There is a “reasonable possibility” that the AE was caused by the investigational product administered, meaning that there is evidence or arguments to suggest a causal relationship

Note: By convention, all AEs reported at the injection site (whether solicited or unsolicited) and all solicited systemic AEs are considered to be related to the administered product and therefore are referred to as reactions and do not require the Investigator’s opinion on relatedness.

Adverse events likely to be related to the product, whether serious or not, that persist at the end of the study will be followed up by the Investigator until their complete disappearance or the stabilization of the subject’s condition. The Investigator will inform the Sponsor of the date of final disappearance of the event or the date of “chronicity” establishment.

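### The SAP's term list for 'Exfoliative dermatitis' is mostly plain site rash and site dermatitis, so the grouped count under that label can mislead

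*SAP*

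**What the plan says.** Protocol 5.1.6 (repeated in the Synopsis) lists findings to be looked for in the Stage I early safety data review (ESDR) before infants are enrolled. One is "Any signs of injection site necrosis or exfoliative dermatitis". It has no rate threshold, unlike the fever item, "Grade 3 fever reported in more than 10% of subjects". The consequence of meeting an item is stated: "If any of the above criteria are met, a decision based on the SMT and DMC recommendations will be made".

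SAP 4.3.1.3.1 turns this into a derived endpoint. It says that for the ESDR "a specific focus will be done on the following events: Injection site necrosis and Exfoliative dermatitis", and then: "These events will be identified also in the main statistical analysis among reported unsolicited AE using the following MedDRA preferred terms". The row for 'Exfoliative dermatitis' opens with "Dermatitis exfoliative, Dermatitis exfoliative generalised, Exfoliative rash, Injection site rash, Vaccination site rash, Application site rash" and ends with "Injection site dermatitis, Vaccination site dermatitis, Application site dermatitis, Administration site dermatitis". The row for 'Injection site necrosis' has eight terms. Four of them (Necrosis, Skin necrosis, Soft tissue necrosis, Extremity necrosis) carry no site qualifier.

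The section does not call the lists a screening search, has no narrow tier, and asks for no check of the reported verbatim.

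**The concern.** A case definition should contain the event it is named for. Here most of the terms under 'Exfoliative dermatitis' describe a rash or dermatitis at the administration site with nothing said about exfoliation. Followed literally, the SAP reports a child coded to Injection site rash as a case of exfoliative dermatitis.

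What is at stake is the reading of a pre-specified safety focus event. A grouped count of, say, three could mean three exfoliative cases or three trivial rashes, and a comparison of SP0202 groups with Prevnar 13 on that row carries the same ambiguity. If the same list also served the ESDR, an ordinary rash could be put before the Safety Management Team (SMT) and the data monitoring committee (DMC) under a label it does not deserve.

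**Working it through.** The plan gives no event rate or power figure for this endpoint, so there is no stated number to reproduce. The check is a count, a comparison of passages and a labelled illustration.

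**1. Terms under 'Exfoliative dermatitis' (SAP 4.3.1.3.1).**

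| Type of term | Number |
|---|---|
| Names exfoliation | 3 |
| Site rash (injection, vaccination, application) | 3 |
| Site dermatitis (injection, vaccination, application, administration) | 4 |
| Total | 10 |

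Terms with no reference to exfoliation: 3 + 4 = 7, and 7/10 = 70%.

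**2. Terms under 'Injection site necrosis'.** Four are site-specific (injection, vaccination, application and administration site) and four are not, so 4/8 = 50%. This mismatch is milder: every term is still necrosis, and only the location is open.

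**3. Does anything else in the plan narrow the count?**
- Solicited local reactions are tenderness, erythema and swelling (Protocol Table 9.1, SAP Table 4.1). Those are not swept in, but a site rash is collected as an unsolicited event, which is where the list is applied.
- Causality does not filter. Under Protocol 9.1.1.3.5 and SAP 5.3.1.2, every injection-site event is related by convention.
- The list is not restricted to the pneumococcal vaccine site. SAP 4.3.1.3.5 shows that unsolicited injection-site reactions are also recorded in relation to concomitant vaccines.
- SAP 5.6 says no blind review of data was performed, so no confirmation step is found there.

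**4. Does anything let a reader undo the grouping?** Yes. Protocol 12.1.1.2 and SAP 5.1.1.2 tabulate unsolicited events within 30 days by system organ class and preferred term. An Exfoliative rash and an Injection site rash would stand on different lines there.

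**5. Illustration of how easily the row fills with no true case.** Inputs: n = 140 toddlers (Stage I) and an assumed per-child rate p of an event coded to one of the seven plain terms. Because one case is enough to make the row non-zero, P(at least one) = 1 − (1 − p)^n.

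| Assumed p | n = 140 | n = 70 |
|---|---|---|
| 0.1% | 1 − 0.999^140 = 0.131 | 1 − 0.999^70 = 0.068 |
| 0.5% | 1 − 0.995^140 = 0.504 | 1 − 0.995^70 = 0.296 |
| 1% | 1 − 0.99^140 = 0.755 | 1 − 0.99^70 = 0.505 |

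The share of toddlers needed for the ESDR is blacked out in SAP 5.4, so 140 is the maximum and 70 is only an example of a smaller review. For contrast, the fever item needs more than 10% of subjects, which is more than 14 of 140.

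**The case against.** The strongest reply is that this is a broad descriptive grouping and little depends on it. All analyses are descriptive, the rows sit under other safety endpoints rather than among SAEs or AESIs, and a sensitive list is a reasonable choice for rare local events that start as parent-reported verbatims. That defends collecting the seven terms. It does not defend reporting them under a name that none of them carries, since the SAP never says the list is deliberately broad.

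Three stronger readings are tempting, and the objection is right to resist them.

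- *A reader might infer that one injection-site rash meets the ESDR criterion and could hold up infant enrolment.* The sentence that introduces the terms ties them explicitly to the main analysis. Their use in the ESDR is suggested by the opening of the section and the word 'also', but neither document says that a term match alone meets the criterion. A met criterion leads to a decision based on SMT and DMC recommendations, not an automatic stop. The DMC charter, which is not among the documents, may add a definition. The ESDR also reviews all related unsolicited events, so a local rash would probably reach the reviewers anyway.
- *A reader might infer that the report could not show whether the feared event occurred.* The preferred-term tables answer that.
- *A reader might infer that such rashes are common and the row is nearly certain to be populated, above all in 700 infants.* No rate appears in either document, and the infant total has no bearing on a criterion that is applied before infants are enrolled.

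Timing also counts. SAP 5.1.3 refers in the past tense to infants enrolled before protocol Version 5.0, so the Stage I review seems to have preceded this SAP text. A change now would serve the report, and possibly later DMC looks.

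**Conclusion.** The point holds as a mismatch between label and content. Seven of the ten terms under 'Exfoliative dermatitis', and to a lesser degree four of the eight under 'Injection site necrosis', do not describe the event named, and the SAP applies them without any qualifier. The grouped count can consist entirely of ordinary local rash and does not correspond to the protocol's focus event.

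The consequence is a misleading grouped safety count. Only if the same list is used in the ESDR does it add possible false flags, which the SMT and DMC would have to sort out. It does not touch the immunogenicity endpoints or the validity of the trial.

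The term counts rest on the SAP alone. The frequency is unknown: roughly 13% to 76% for at least one such case in 140 toddlers depends wholly on the assumed 0.1% to 1% rate, and falls if fewer toddlers are reviewed.

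**What to change.** Keep all the terms and report them in separate rows of the SAP 4.3.1.3.1 table:

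- 'Exfoliative dermatitis': Dermatitis exfoliative; Dermatitis exfoliative generalised; Exfoliative rash.
- 'Injection site rash/dermatitis, not specified as exfoliative': the other seven terms.
- 'Injection site necrosis': the four site-specific terms.
- 'Necrosis, site not specified': the four remaining terms.

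No adjudication step is needed, and none should be added for this purpose, because the SAP defines no such process for the main analysis.

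The cost is a short SAP edit and extra table rows. The small downside is that a true exfoliative case coded to a non-specific term would appear in the second row rather than the first. It stays visible there and in the preferred-term tables.

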#### **4.3.1.3.2 Action Taken**

This information will be summarized as collected, including missing observations. No derivation or imputation will be done.

#### **4.3.1.3.3 Seriousness**

This information will be summarized as collected. No derivation or imputation will be done.

#### **4.3.1.3.4 Outcome**

This information will be summarized as collected. No derivation or imputation will be done.

#### **4.3.1.3.5 Causal Relationship**

This information will be summarized as collected in the field “Relationship to Investigational Product”. Missing causal relationship will be handled as described in Section 5.3.1.2. Relationship to non-investigational product (ie, Concomitant vaccines) is collected for the Unsolicited Injection Sites Reactions and be presented in summary tables and in the listings. Relationship to study procedure for SAE is only presented in the listings.

#### **4.3.1.3.6 AEs Leading to Study Discontinuation**

This information will be summarized as collected. A flag is available in the clinical database for all AEs in order to identify AEs leading to discontinuation before the end of active phase.

In general, the items that are counted are:

- Disposition table: A participant who, on the “Completion at End of Study” form question “What was the participant's status?” has “Adverse Event” checked.
- Safety overview table: A participant who has either on the “Completion at End of Study” form, question “What was the participant's status?” has “Adverse Event” checked or lists a solicited AE that has “Caused Study Termination” checked that is at least Grade 1 or an unsolicited AE that has “Caused Study Discontinuation” checked that is at least Grade 1 or missing and is within the time period indicated.
- SOC/PT table: A solicited AE that has “Caused Study Termination” checked that is at least Grade 1 or an unsolicited AE that has “Caused Study Discontinuation” checked that is at least Grade 1 or missing and is within the time period indicated.

### **4.3.2 Immunogenicity**

#### **4.3.2.1 Computed Values for Analysis**

In order to appropriately manage extreme values ('< LLOQ' and '≥ ULOQ'), lower limit of quantitation and upper limit of quantitation, respectively, for analysis purposes of Geometric Mean Titer (GMTs) / Geometric Mean Concentration (GMCs) and percentage above cut-offs, the following computational rules will be applied to the values provided in the clinical database:

- If a value is '<LLOQ', then the computed value is LLOQ/2
- If a value is ' $\geq$  ULOQ' or ' $>$ ULQ', then the computed value is ULOQ
- otherwise, the computed value is the value

#### 4.3.2.2 Thresholds

Generally, if the computed value is  $\geq x$ , then the derived indicator will be “Yes” for that test, otherwise indicator will be "No". Note: If the computed value is missing, indicator will be missing. The thresholds are summarized in the tables below:

**Table 4.5: Immunogenicity Thresholds of interest for Stage 1/ Toddlers**

Endpoints	Baseline (V01)	30 days post-injection (V02)
Pneumococcal serotype specific binding IgG	$\geq 0.35 \mu\text{g/mL}$	$\geq 0.35 \mu\text{g/mL}$
Pneumococcal serotype specific functional Ab (OPA)	$\geq \text{LLOQ (1/dil)}$	$\geq \text{LLOQ (1/dil)}$
Anti-diphtheria and anti-tetanus Ab	$\geq 0.1 \text{ IU/mL}$ , $\geq 1.0 \text{ IU/mL}$	$\geq 0.1 \text{ IU/mL}$ , $\geq 1.0 \text{ IU/mL}$
Anti-poliovirus 1, 2, and 3 Ab	$\geq 8 \text{ (1/dil)}$	$\geq 8 \text{ (1/dil)}$
Anti-PRP Ab	$\geq 0.15 \mu\text{g/mL}$ $\geq 1.0 \mu\text{g/mL}$	$\geq 0.15 \mu\text{g/mL}$ $\geq 1.0 \mu\text{g/mL}$

**Table 4.6: Immunogenicity Thresholds of interest for Stage 2/ Infants**

Endpoints	Baseline (V01)*	30 days post- Dose 3 (V04)	Before Dose 4 (V05)	30 days post- Dose 4 (V06)
Pneumococcal serotype specific binding IgG	$\geq 0.35 \mu\text{g/mL}$	$\geq 0.35 \mu\text{g/mL}$	$\geq 0.35 \mu\text{g/mL}$	$\geq 0.35 \mu\text{g/mL}$
Pneumococcal serotype specific functional Ab (OPA)		$\geq \text{LLOQ (1/dil)}$	$\geq \text{LLOQ (1/dil)}$	$\geq \text{LLOQ (1/dil)}$
Anti-diphtheria and anti- tetanus Ab	$\geq 0.01 \text{ IU/mL}$ , $\geq 0.1 \text{ IU/ mL}$ , $\geq 1.0 \text{ IU/mL}$	$\geq 0.01 \text{ IU/mL}$ , $\geq 0.1 \text{ IU/ mL}$ , $\geq 1.0 \text{ IU/mL}$		
Anti-poliovirus 1, 2, and 3 Ab	-	$\geq 8 \text{ (1/dil)}$		
Anti-PRP Ab	-	$\geq 0.15 \mu\text{g/mL}$ $\geq 1.0 \mu\text{g/mL}$		
Anti-hepatitis B Ab	-	$\geq 10 \text{ mIU/mL}$ $\geq 100 \text{ mIU/mL}$		
Anti-measles Ab			-	$\geq 255 \text{ mIU/mL}$
Anti-mumps Ab			-	$\geq 10 \text{ mumps Ab U/mL}$
Anti-rubella Ab			-	$\geq 10 \text{ IU/mL}$
Anti-varicella Ab			-	$\geq 5 \text{ glycoprotein units/mL}$

#### 4.3.2.3 Fold-rise

The derived endpoint fold-rise is driven by both baseline and post-baseline computed values. The following algorithm will be used to minimize the numerator and maximize the denominator.

- If the baseline computed value is < LLOQ and the post-baseline computed value is < LLOQ then the fold-rise is 1

\* Not applicable from protocol version 5.0

- If the baseline computed value is  $\geq$  LLOQ and the post-baseline computed value is  $\geq$  LLOQ then the fold-rise is post-baseline computed value / baseline computed value
- If the baseline computed value is  $\geq$  LLOQ and the post-baseline computed value is  $<$  LLOQ then the fold-rise is (LLOQ/2) / baseline computed value
- If the baseline computed value is  $<$  LLOQ and the post-baseline computed value is  $\geq$  LLOQ then the fold-rise is post-baseline computed value /LLOQ

If the computed value is  $\geq$  X-fold rises, then the derived  $\geq$  X fold rises indicator will be "Yes" for that test, otherwise  $\geq$  X-fold rises will be "No".

Note: If baseline or post-baseline is missing, then fold-rise is missing.

#### **4.3.2.4 Seroconversion**

Not applicable.

#### **4.3.2.5 Vaccine Response**

Vaccine Response is to be derived for each anti-pertussis antigens (PT, FHA, PRN, and FIM) Ab concentrations as follow:

- Pre-vaccination  $<$  LLOQ, then post-vaccination should be  $\geq$  4x the LLOQ
- Pre-vaccination  $\geq$  LLOQ but  $<$  4x the LLOQ, then post-vaccination should achieve a 4-fold rise (post- vaccination/pre-vaccination  $\geq$  4)
- Pre-vaccination  $\geq$  4x the LLOQ, then post-vaccination should achieve a 2-fold response (post-vaccination/pre-vaccination  $\geq$  2)

Pre vaccination concentrations  $<$  LLOQ will be converted to LLOQ for purposes of calculating this vaccine response. If the pre-vaccination concentration is missing or No Result (NR) or if the post-vaccination concentration is missing or NR, then the vaccine response is missing.

#### **4.3.3 Efficacy**

Not applicable.

#### **4.3.4 Derived Other Variables**

##### **4.3.4.1 Age for Demographics**

Calendar age will be use in the analysis expressed in Months for Stage I participants and Days/Weeks for Stage II participants.

#### **4.3.4.2 Duration of the Study**

The duration will be computed in days as follows: Latest period date - earliest period date + 1.

For Infants, primary series duration will be calculated as follows:

[Date of latest Visit 04 - date of earliest Visit 01] + 1

And booster phase duration will be calculated as follows:

[Date of latest Visit 06 - date of earliest Visit 05] + 1

#### **4.3.4.3 Participant Duration**

The duration of a participant participation in the study will be computed as follows:

Maximum (Visit dates, Termination date, Follow-up date, Last contact date) - V01 date + 1.

For infant's primary series, the duration of participant participation will be computed as follows:

[Maximum (Visit dates (Visit 01 up to Visit 04), Termination date (if prematurely withdrawn before the 3rd vaccination), Last contact date (if prematurely withdrawn after the 3rd vaccination and before the 4th vaccination)) - Visit 01 date] + 1.

For the booster phase, the duration of participant participation will be computed as follows:

[Maximum (Visit dates (Visit 05 up to Visit 06), Termination date (if prematurely withdrawn post 4th vaccination), Last contact date)) - Visit 05 date] + 1.

## **5 Statistical Methods and Determination of Sample Size**

The statistical analyses will be performed under the responsibility of the Sponsor's Biostatistics platform using SAS® Version 9.4 software or later.

The results of the statistical analysis will be available in the final clinical study report (CSR).

For descriptive purposes, the following statistics will be presented:

**Table 5.1: Descriptive statistics produced**

Baseline characteristics and follow-up description	Categorical data	Number of participants. Percentage of participants.
	Continuous data	Mean, standard deviation, quartiles, minimum, and maximum.
Clinical safety results	Categorical data	Solicited: Number and percentage (95% CIs) of participants. Unsolicited: Number and percentage (95% CIs) of participants, and number of events.
Immunogenicity results	Categorical data (seroprotection, cutoff, thresholds)	Number and percentage (95% CIs) of participants.
	Continuous data (titer / data)	Log10: Mean and standard deviation. Anti-Log10 (work on Log10 distribution, and anti-Log10 applied): Geometric mean, 95% CI of the geometric mean, quartiles, minimum, and maximum. Graphical representation by Reverse Cumulative Distribution Curve (RCDC). Boxplots and Forest plots.

The CI for the single proportion will be calculated using the exact binomial method (Clopper-Pearson method, quoted by Newcombe (2)), ie, using the inverse of the beta integral with SAS®.

For immunogenicity results, assuming that Log10 transformation of the titers / concentrations follows a normal distribution, at first, the mean and the 95% CI will be calculated on Log10 (titers / data) using the usual calculation for normal distribution (using Student's t distribution with n-1 degree of freedom), then antilog transformations will be applied to the results of calculations, in order to provide geometric means (GMs) and their 95% CI.

CIs of the difference of proportions between 2 groups will be computed using the Wilson Score method without continuity correction. CIs of ratio of GMTs / GMCs between 2 groups will be computed from the difference in means of log10 transformed titers/concentrations between 2 groups with normal approximation.

